2 INTRODUCTION

Presbyopia is the gradual loss of the eyes' ability to focus on nearby objects and typically starts in patients around 40 years of age and continues to worsen over the next 20 years. This requires a frequent adjustment of the near prescription and as a result multifocal soft contact lenses are available with increasing near add increments. New lens materials and multifocal lens designs are introduced to the marked frequently and it is of interest to understand how these perform in comparison to existing products.

CooperVision is interested to better understand the performance of their own frequent replacement lens Biofinity Multifocal (CONTROL) in comparison to the competitor product TOTAL30 multifocal (TEST), which has recently been launched by Alcon Inc.

3 OBJECTIVES

The objective of the study is to compare the lens performance of CONTROL and TEST.

The primary outcome variable for this study is:

 'Lens handling for insertion', using a 0-100 scale, collected in office after 1 month of study lens wear.

Also of interest are subjective feedback on comfort, vision and overall performance using ratings, agreement questions and preferences.

4 HYPOTHESIS

H₀. There is no statistical difference in lens handling for insertion after 1-month of wear between the Biofinity multifocal and TOTAL 30 multifocal lenses.

H₁. There is a statistical difference in lens handling for insertion after 1-month of wear between the Biofinity multifocal and TOTAL 30 multifocal lenses.

5 MATERIALS AND METHODS

5.1 STUDY DESIGN

5.1.1 OVERALL DESIGN

This is a prospective, randomized, participant-masked, crossover, bilateral dispensing study conducted at approximately 5 clinical practice sites in the United States and Canada. Each lens type will be worn for approximately 4-6 weeks: the lens prescription of each lens type will be

optimized after 3-10 days wearing experience, prior to starting a 1-month (28-32 days) wear period.

5.1.2 RANDOMIZATION

Participants will wear the CONTROL and TEST lenses in a randomized order.

A randomization schedule will be generated for each site using a web-based program (for example, www.randomization.com or similar). to determine the order CONTROL and TEST lens wear. The final study randomization schedule will be generated by CORE's Database Administrator and provided to each site.

5.1.3 MASKING

Lens packages/foils will be over-labeled with strongly adhesive stickers to mask the participant to the lens brand.

It is not possible for the study investigators to be masked because of the need to follow the specific lens fitting guide during the lens prescription optimization visit (Visits 0, 1-1, 2-1).

5.2 INVESTIGATIONAL SITES

5.2.1 NUMBER OF SITES

This study will be conducted at approximately 5 optometry practice sites in the US and Canada.

5.2.2 INVESTIGATOR RECRUITMENT

The principal investigator at each site will be required to fulfil the following criteria:

- Is a licensed Optometrist with at least two years of contact lens fitting experience.
- Can demonstrate training in Good Clinical Practice (GCP) by the already trained principal investigator.
- Accepts responsibility for the conduct of the study at their site.
- Has in-office email and either document scanning capabilities or fax.
- Will scan and send all study visit documents to CORE, ideally the same day* as the visit or at most within 2 days of the study visit.
- Is willing to follow the study protocol and to co-operate with the study monitors at CORE.

^{*} Study documents are required as soon as possible because this allows for a timely data review, query and entry.

5.3 STUDY POPULATION

5.3.1 SAMPLE SIZE CALCULATION

The sample size was calculated using lens handling data from a previous study comparing Lens A against lens B (CooperVision, data on file). In that study a 0-100 scale was also used and a target difference of 5 units on the 0-100 scale was chosen as a meaningful clinical difference in 0-100 subjective responses.

Using the 0-100 scale data described above for 'lens handling for insertion', where the data showed a standard deviation of 12.7 and when applying requirements of 80% power and alpha 0.05 in a two-tailed t-test, a minimum sample size of 53 participants is recommended in order to detect a mean difference of 5 units.

To account for dropout, up to 60 participants may be randomized and dispensed with study product in total, with the target of at least 53 completing the study.

[figure not shown]

Figure 1: Sample size calculation graph

5.3.2 NUMBER OF PARTICIPANTS

Participants will be recruited using site records, databases and advertising materials (e.g., posters, email scripts) approved by the ethics review board. All initial individual-targeted recruitment activities, such as any direct mailing of recruitment scripts, will be conducted by practice staff that are not directly involved in conducting the research. This separation will reduce any undue influence of the optometrist-patient relationship. This process will also eliminate opportunity for the investigator to access personal health information before any consent for disclosure is provided by the potential participant.

It is anticipated that up to 80 potential participants may attend a Screening visit and approximately 60 participants may be randomized and dispensed with study products, with a target of 53 completing the study.

5.3.3 INCLUSION AND EXCLUSION CRITERIA

A person is eligible for inclusion in the study if he/she:

- 1. Is at least 42 years of age and has full legal capacity to volunteer;
- 2. Has read and signed an information consent letter;
- 3. Self reports having a full eye examination in the previous two years;
- 4. Anticipates being able to wear the study lenses for at least 8 hours a day, 5 days a week;
- 5. Is willing and able to follow instructions and maintain the appointment schedule;
- 6. Habitually wears spherical multifocal soft contact lenses, for the past 3 months minimum[^];
 - Maximum of 4 participants (out of 12) per site may be habitual wearers of daily disposable lenses,
 - Maximum of 4 participants (out of 12) per site may be habitual wearers of Biofinity Multifocal.
 - Maximum of 4 participants (out of 12) per site may be habitual wearers of either TOTAL30 Multifocal or AirOptix plus HydraGlyde Multifocal
- 7. Has refractive astigmatism no higher than -0.75DC;
- 8. Is presbyopic and requires a reading addition of at least +0.75D and no more than +2.50D;
- 9. Can be fit and achieve binocular distance vision of at least 20/30 Snellen which participants also deem to be 'acceptable', with the available study lens parameters (Distance sphere +4 to -6; near addition as per study design).

^Exceptions may be permitted after discussion with the study monitor or sponsor to target the anticipated habitual lens distribution across all sites. If necessary, additional exceptions may be permitted after discussion with the study monitor or sponsor.

A person will be excluded from the study if he/she:

1. Is participating in any concurrent clinical or research trial;

- 2. Has any known active* ocular disease and/or infection that contraindicates contact lens wear:
- 3. Has a systemic condition that in the opinion of the investigator may affect a study outcome variable:
- 4. Is using any systemic or topical medications that in the opinion of the investigator may affect contact lens wear or a study outcome variable;
- 5. Has known sensitivity to the diagnostic sodium fluorescein used in the study;
- 6. Self-reports as pregnant, lactating or planning a pregnancy at the time of enrolment;
- 7. Has undergone refractive error surgery or intraocular surgery.
- * For the purposes of this study, active ocular disease is defined as infection or inflammation which requires therapeutic treatment. Mild (i.e. not considered clinically relevant) lid abnormalities (blepharitis, meibomian gland dysfunction, papillae), corneal and conjunctival staining and dry eye are not considered active ocular disease. Neovascularization and corneal scars are the result of previous hypoxia, infection or inflammation and are therefore not active.

Age ≥42 years is an inclusion criterion because presbyopia is unlikely in persons aged <42 years and, if present, may not be due solely to presbyopic changes representative of the wider population.

Pregnant and lactating women are not being excluded from the study due to safety concerns but due to fluctuations in refractive error, accommodation and/ or visual acuity that occur secondary to systemic hormonal changes. It has further been shown that pregnancy could impact tear production, which could impact dry eye symptoms. Such fluctuations could affect data, thereby negatively affecting study data integrity.

5.4 STUDY MATERIALS

Each site will have an inventory of the CONTROL lens on site which will be used for fitting and dispensing the CONTROL lens.

For the TEST lens, trial lenses for the fitting can either be ordered based on the participant's refraction and/or latest contact lens prescription or a fitting set of the test lens may be used if available. Following a successful lens fit commercial TEST lenses will be ordered.

Reimbursement to practice sites for study product expenses will be provided by CooperVision during or at the end of the study, after CORE has reconciled the invoices and the product accountability and dispensing logs.

CORE will provide all sites with the study paperwork. This will include participant informed consent letters and study data collection forms, product accountability logs and the participant dispensing logs. CORE will train site personnel to complete the forms correctly and provide continued support to answer queries on correct form completion.

5.4.1 LENSES

Both lens types are commercially available in the US and Canada.

The table below lists the contact lens details for the CONTROL and TEST lenses including the lens parameters available for this study.

Lens	CONTROL	TEST
Manufacturer	CooperVision	Alcon Inc.
Material	comfilcon A	lehfilcon A
FDA Class	Group 5	Group 5
Sphere power (D)	+4.00 to -6.00 (0.25 steps)	+4.00 to -6.00 (0.25 steps)
ADD power (D)	+1.00D, +1.50D, +2.00D, +2.50D, +2.00N, +2.50N	HI, MED, LO
Base curve (mm)	8.6	8.4
Diameter (mm)	14.0	14.2

Table 1: Lens characteristics & parameter to be used

5.4.2 LENS CARE PRODUCTS

It is expected that participants will continue to use their habitual soft lens care products with the study lenses. This will avoid any potential incompatibility the participants may have with a new care product. Each participant will be compensated for them using their own lens care product for the approximately 3-month study period. Participants who habitually use a daily disposable lens or use a care regimen that is not suitable with the use of the study lenses, will be provided with OptiFree Puremoist (Alcon). The sites will source commercial bottles of this care product and reimbursement will be provided by CooperVision, after CORE has reconciled the invoices and the product accountability and dispensing logs.

5.4.3 OTHER PRODUCTS

Sodium fluorescein will be used to assess corneal and conjunctival staining.

5.4.4 REWETTING DROPS

Participants will not be encouraged to use rewetting drops; however, those who habitually used rewetting drops will be allowed to continue using their normal drops.

5.4.5 DISPOSING OF STUDY PRODUCTS

At the end of the study, all sites will return all unused products to CORE, unless otherwise directed. Worn lenses will be disposed of by participants and at the sites according to local regulations.

5.4.6 PRODUCT ACCOUNTABILITY

Accountability logs are to be completed to record all study products that were used for each participant, which includes products used during the visits and those dispensed to and returned by each participant.

5.5 SCHEDULED AND UNSCHEDULED VISITS

This study has a minimum of 9 scheduled study visits, including the screening visit, though some visits may be scheduled concurrently on the same day. There is an option for repeated screening and lens fitting visits as needed. Some of the scheduled visits can occur on the same day, participants are therefore required to only attend 6 or 7 in-office visits.

A scheduled follow-up visit may only take place when the participant attends wearing the study lenses for at least two hours. If this is not the case and the participant is not experiencing any problems with the lenses, the appointment will be rescheduled, ideally within the visit window.

Visits that fall outside of the specified visit windows will be designated as protocol deviations and at the end of the study, the data collected during protocol deviations will be assessed for their suitability to be included in the analysis population.

Table 3 summarizes the scheduled study visits and study codes.

Table 2: Summary of visits

Visit code	Approximate Duration	Visits
0	2 hr	Screening & Fitting of study lenses
0/R1, 0/R2	As needed	Repeat Visit 0 if needed
Phase 1		
1-0	0.5 hr	Dispense Pair #1
1-1	0.5 hr	Optimize Pair #1 (Phase 1, 3-10 days after 1-0)
1-2	0.5 hr	Dispense (optimized) Pair #1
1-3	1.0 hr	1-month follow-up Pair #1 (Phase 1, 28-32 days after 1-2)
Phase 2		
2-0	0.5 hr	Dispense Pair #2 (Phase 2, same day as 1-3)
2-1	0.5 hr	Optimize Pair #2 (Phase 2, 3-10 days after 2-0)
2-2	0.5 hr	Dispense (optimized) Pair #2
2-3	1.0 hr	1-month follow-up Pair #2 (Phase 2, 28-32 days after 2-2)
EXIT	N/A	Exit VA, exit forms & remuneration

Pair #1 and #2 will be either CONTROL or TEST, as determined by the randomization table.

*Visits could be subsequent on same day if CL power is unchanged or dispense lenses are available on site.

5.5.1 VISIT 0, SCREENING & FITTING VISIT

Informed consent shall be obtained in writing from the participant and the process shall be documented before any procedure specific to the clinical investigation is carried out.

[figure not shown]
Participants will be assigned a unique alpha-numeric study ID after they sign the consent documentation i.e., before their eligibility for the study has been confirmed. Each site will use a different letter preceding the participant ID number. For example, participant 01 at site W will be W01, and participant 01 at site Z will be Z01. Ineligible participants will be discontinued from the study.

The investigator will determine participant eligibility using the inclusion and exclusion criteria. The study procedures are outlined below:

- 1. The participant is expected to insert their habitual multifocal contact lenses at least 2 hours before attending the visit
- 2. The participant will be required to read and sign an Informed Consent Form prior to enrollment. When the participant has signed the consent form, the participant will be considered enrolled in the study and will be assigned a study ID.
- 3. Participant demographics and medical history (age, sex, medical conditions, medications, allergies).

4. Contact lens history (habitual lens information and wearing habits).

- 5.
- 6. The participant removes their habitual contact lenses.
- 7.
- 8.
- 9.
- 10.

12. The investigator will fit both study lenses (CONTROL and TEST) using the provided lenses (CONTROL) or using the office fitting set or pre-ordered fitting lenses (TEST). The manufacturers fitting guidelines will be followed.

- 13. The investigator will confirm that the participant meets the eligibility specifications set out in the inclusion criteria and exclusion criteria and is eligible to continue in the study.
- 14. If additional fitting lenses need to be ordered to determine the final lens power, schedule a re-screening visit. Both study lenses have to be tested on eye in the final power before any of the study lens types can be dispensed.

5.5.2 REPEATED SCREENING VISITS (VISIT 0/R1 OR VISIT 0/R2)

In some circumstances a repeated screening may need to be scheduled. Examples include, but are not limited to:

- 1. Incomplete information available at time of screening to determine eligibility (e.g., current lens brands worn, history from current eye care practitioner etc.)
- 2. Study procedures unable to be completed in time scheduled for visit;
- 3. Study products not available at the time of the screening visit;
- 4. A transient health condition which may affect the eye(s) (e.g., a common cold, active allergies, fatigue etc.)
- 5. The short-term use of medications (e.g., antibiotics, antihistamines etc.)
- 6. Reassessment of baseline ocular conditions (e.g., corneal and/or conjunctival staining, scars etc.)

The maximum total number of screenings permitted will be 3, the initial and two repeat screening visits.

5.5.3 VISIT 1-0 DISPENSE LENS PAIR #1

This visit may or may not be subsequent to the screening visit, depending on lens availability. (A full inventory of the control lenses will be available at the site, however the test lens must likely be ordered first – do NOT dispense fitting lenses of the TEST lens, only purchased lens supply is acceptable for dispense even during the optimization wear phase.)

Procedures as follows:

1.	Confirm participant's health and medications are unchanged.
2.	
3.	
1	

5. A	Assess	lens f	it:	determine	lens	centration	and	overall	acceptability	١.
------	--------	--------	-----	-----------	------	------------	-----	---------	---------------	----

6.7.

[figure not shown]
- 8. The participant will receive a pair of study lenses for dispense (and a backup pair if needed) and will be instructed to wear the lenses for at least 8 hours a day, 5 days a week.
- 9. The participant will be instructed to use their habitual lens care products with the study lenses or if applicable as per section 5.4.2, will be dispensed with a monthly supply of Optifree Puremoist the correct use of the product will be reviewed with the participant prior to dispense.
- 10. Visit 1-1 will be scheduled.

5.5.4 VISIT 1-1 OPTIMIZE PAIR #1

[figure not shown]
Participants will be asked to insert study lenses at least 2 hours prior to the visit.

This visit will occur 3-10 days (inclusive) after visit 1-0.

- 1. Confirm participant's health and medications are unchanged.
- 2. Ask participant about lens performance for acceptability of contact lens comfort and vision at distance and near.

5. Assess lens fit: determine lens centration and overall acceptability.

8. Remove lenses

9.

7. If no power change is needed and if at least two pairs of optimized lenses (One pair for dispense, one pair as a backup if needed) are available on site continue with visit 1-2 concurrently. Otherwise order the new power lenses and schedule Visit 1-2 for another time. If new lenses need to be ordered, participants will be allowed to wear habitual MF lenses in the meantime.

5.5.5 VISIT 1-2 DISPENSE (OPTIMIZED) PAIR #1

This visit may be conducted immediately following Visit 1-1 (if no prescription change is needed) or can be scheduled after Visit 1-1.

Participant to attend this visit wearing spectacles.

Procedures as follows:

1.	Confirm participant's health and medications are unchanged.
2.	
3.	
4.	
5.	
1.	Ensure vision at distance and near is acceptable for participant.
2.	Assess lens fit: determine lens centration and overall acceptability.
2	
3.	
3.	
 3. 4. 	
4.	
4.	

6. The participant will be scheduled to return for Visit 1-3.

5.5.6 VISIT 1-3, 1-MONTH FOLLOW-UP PAIR #1

Participants will be asked to insert study lenses at least 2 hours prior to the visit.

This visit will occur 28-32 days (inclusive) after visit 1-2.

- 1. Confirm participant's health and medications are unchanged.
- 2. Ask participant about lens performance for acceptability of contact lens comfort and vision at distance and near.
- 3.
- 4. Ask participant to complete the 'Subjective ratings at visit' and 'Experience survey'.
- 5.
- 6. Assess lens fit: determine lens centration and overall acceptability.
- 7.
- 8.
- 9. Continue with visit 2-0.

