5.5.10 VISIT 2-3, 1-MONTH FOLLOW-UP PAIR #2

Participants will be asked to insert study lenses at least 2 hours prior to the visit.

This visit will occur 28-32 days (inclusive) after visit 2-2.

Assessments of Pair #2 will be conducted as described for Pair #1 at visit (Visit 1-3).

Participants will be asked to complete a 'Preference questionnaire' to compare between Lens Pair #1 and Lens Pair #2.

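### At both 1-month visits, site staff who are not masked ask about comfort and vision before the participant fills in the rating forms; the forms should come first

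*Combined protocol and SAP*

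**What the plan says.** Section 5.1.1 describes the design: "This is a prospective, randomized, participant-masked, crossover, bilateral dispensing study". Section 5.1.3 states that "It is not possible for the study investigators to be masked because of the need to follow the specific lens fitting guide", and ties this to Visits 0, 1-1 and 2-1. Masking is by over-labelled packaging and is aimed at the participant. No readable text masks any other person at the site.

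The primary outcome in section 3 is "Lens handling for insertion', using a 0-100 scale, collected in office after 1 month of study lens wear". The same section adds: "Also of interest are subjective feedback on comfort, vision and overall performance using ratings, agreement questions and preferences". Section 12.1 plans equivalence tests on ratings of comfort, dryness, vision clarity and overall satisfaction, with a margin of 7 units.

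The readable steps of Visit 1-3 (section 5.5.6) run in this order:

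- Step 1: health and medication check.
- Step 2: "Ask participant about lens performance for acceptability of contact lens comfort and vision at distance and near".
- Step 3: not readable.
- Step 4: "Ask participant to complete the 'Subjective ratings at visit' and 'Experience survey".
- Step 6: lens fit assessment.

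For Visit 2-3, section 5.5.10 says "Assessments of Pair #2 will be conducted as described for Pair #1 at visit (Visit 1-3", and adds a preference questionnaire without giving it a place in the sequence.

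**The concern.** The ratings are the participant's own judgement, so their main protection is that the participant does not know the brand. A spoken exchange about comfort and vision just before the forms puts that judgement next to someone who may know it. How the question is put, or how the answer is received, could then differ between the sponsor's lens and the competitor's.

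The crossover does not remove such an effect. An influence that is the same for both lenses cancels in the within-participant difference. One attached to a particular lens follows it into whichever period it is worn, and goes straight into the estimated difference.

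The reason given for not masking investigators is the fitting guide, at visits other than 1-3 and 2-3. That reason does not require performance to be discussed before it is rated.

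**Working it through.** **Order of events.** The numbering of steps 2 and 4 is readable, so the missing step 3 does not put the order in doubt. Section 5.5.10 carries the order into the second period. Neither section tells the participant to complete the forms before discussion or away from staff.

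**Overlap between the question and the outcomes.**

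| Outcome | Covered by step 2? | Route |
|---|---|---|
| Comfort rating (equivalence, ±7) | Yes | Direct |
| Vision clarity rating (equivalence, ±7) | Yes | Direct |
| Dryness and overall satisfaction (equivalence, ±7) | Not named | Related to the topics raised |
| Insertion handling (primary) | No | Indirect |

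**The plan's own sample size.** Inputs from section 5.3.1: SD 12.7, difference 5, two-sided alpha 0.05, power 80%. Taking 12.7 as the SD of the within-participant difference (an assumption, as the protocol does not say), a paired t-test has noncentrality 5 ÷ 12.7 × √n. At n = 52 the power is 79.5% and at n = 53 it is 80.3%, so the stated 53 is reproduced.

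**Sensitivity to a lens-specific shift.** The documents give no size for any shift, so the values below are assumed, to show how the design responds. They do not estimate bias in this trial. The only SD available is for handling, where the route is indirect; none is given for comfort or vision.

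- Standard error of the mean difference: 12.7 ÷ √53 = 1.74 units.
- Type I error with shift b: the power formula at n = 53 with b in place of 5.
- Power for a true 5-unit difference opposed by the shift: the same formula with 5 − b.

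| Assumed shift b | Two-sided type I error | Power for a true 5 units |
|---|---|---|
| 0 | 5.0% | 80.3% |
| 0.5 | 5.9% | 71.6% |
| 1 | 8.7% | 61.4% |
| 2 | 20.3% | 39.3% |
| 3 | 39.3% | 20.3% |

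A shift of this kind is not reduced by recruiting more participants.

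**Effect of re-ordering on the design.** No sample size input, visit, visit window or test changes. The target stays at 53 completers, with up to 60 randomized.

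**The case against.** The case for leaving the order alone has several parts.

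- **No actor is named.** Step 2 does not say who asks. It is one acceptability question, worded identically for both lenses, and nothing has staff reveal the brand or offer an opinion. A reader might infer an interview led by an investigator who knows the lens; the text does not go that far. What stands is that whoever asks is not masked by the protocol.
- **The primary outcome is not the subject of the question.** A reader might infer that the handling score is compromised. The documents do not support that: step 2 does not mention handling, and the forms are not reproduced, so it cannot be confirmed which one carries the handling item. This limits the direct concern to comfort and vision.
- **Not every outcome is a rating.** Visual acuity and the counts of lenses and fit attempts are also planned, and this point does not concern them.
- **Other contact remains.** Staff may have dealt with the participant at earlier visits, and Visit 1-1 asks the same question. Re-ordering closes only the exposure nearest to the rating. This stands as a limit on the benefit.
- **The order is partly sound already.** The ratings precede the readable lens fit assessment. The preference questionnaire has no stated position, so a wrong order cannot be claimed for it.
- **The cost cannot be fully verified.** Step 3 is hidden. Section 5.5 makes a follow-up visit depend on at least two hours' wear and refers to lens problems when rescheduling is considered; step 2 may help with that check. This calls for care in how the steps are moved.

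**Conclusion.** The point holds as a low-cost improvement in conduct, not as a demonstrated bias. The protocol puts a spoken question on comfort and vision ahead of the participant's ratings at both 1-month visits and masks nobody at the site. The route is direct for the comfort and vision ratings, including those tested for equivalence at ±7, and indirect for insertion handling.

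Its size cannot be estimated from the documents. The sensitivity table shows only that the handling comparison would respond to a shift of a unit or two if one existed; nothing in the plan shows that one does, and it would have to differ between lenses to matter.

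The conclusion assumes that step 2 is asked by a member of the site's staff, and that no unreadable text already has the forms completed first.

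**What to change.** At Visits 1-3 and 2-3:

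1. Keep the wear-time check and the step 1 health and medication check first, with any check on problems needed for the visit to proceed.
2. Then have the participant complete the visit ratings and the experience survey unaided, before any discussion of lens performance. In section 5.5.6 this means moving step 4 ahead of step 2.
3. In section 5.5.10, state that the preference questionnaire is also completed before that discussion.

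The cost is a small re-ordering of the visit form. Before adopting it, the sponsor should confirm that step 3 does not depend on the present order. The change leaves earlier contact with unmasked staff as it is, and the report should not present it as extending the masking.
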